6.5 Instructions for initiation of a New Cycle

A new course of treatment may begin on the scheduled Day 1 of a new cycle if:

- The ANC is $\geq 1.0K/\mu L$, or \geq the baseline ANC, if the baseline ANC was $<1.0K/\mu L$.
- The platelet count is $\geq 100K/\mu L$, or \geq the baseline platelet count, if the baseline platelet count was less than $100K/\mu L$.
- Any drug-related rash, neuropathy or cardiac event that may have occurred has resolved to \leq grade 1 severity or baseline.
- Any other drug-related adverse events that may have occurred have resolved to \leq grade 2 severity.

If these conditions are not met on Day 1 of a new cycle, the subject will be evaluated weekly and a new cycle of treatment will not be initiated until the toxicity has resolved as described above. A maximum delay of 21 days is allowed for any given cycle. If these conditions remain unmet on Day 21, the patient is to be taken off of the protocol.

If anti-thrombotic prophylaxis (aspirin, else warfarin or low molecular weight heparin) was held during a given cycle for a platelet count $<50 K/\mu L$, it should be resumed as soon as the platelet count recovers to $\geq 50 K/\mu L$.

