6.4.5 Dose Modification or Interruption

Pomalidomide Dose Reductions

Dose reduction(s) will be allowed for any subject who develops a DLT during Cycle 1 or beyond Cycle 1 who develops a toxicity that, in the opinion of the Investigator, requires a dose-reduction.

For treatment interruptions during a cycle, the (28- or 21-day) schedule of each cycle will continue to be followed. Missed doses of pomalidomide are not made up.

For treatment interruptions that delay the scheduled start of a new cycle, when toxicity has resolved as required to allow the start of a new cycle (Section 6.5), the restart day of therapy becomes Day 1 of the next cycle.

The following table provides the dose reduction sequence for pomalidomide:

Table 2: Schedule of Pomalidomide Dose Reduction

	If the DLT/Toxicity occurred or recurred at --- (mg/dose/d 1-28 or d 1-21 depending on Schedule):	Reduce dose to --- (mg/dose/d 1-28 or d 1-21 depending on Schedule):
Pomalidomide	4	3
	3	2
	2	1
	1	0.5

Dosing interruptions and reductions are not permitted during Cycle 1 unless the subject experiences a DLT. Dose interruptions and reductions are permitted beyond Cycle 2. Examples of possible reasons for and extent of dose modification management are outlined in Table 3. The events listed are not all-inclusive and are based on observations pooled from studies with all compounds in the IMiD® class of drugs. Therefore, these events may occur but are not necessarily expected. The investigator may choose to modify pomalidomide dosing further downward or discontinue pomalidomide treatment for any adverse event.

Study drug may be held (up to 21 days) and subsequent dose reductions made as outlined in Table 3. If study drug needs to be held > 21 days, the patient is to be taken off study. Once a dose has been reduced, it cannot be re-escalated.

At the discretion of the Investigator, the use of G-CSF will be permitted to manage neutropenic fever or a Grade 4 neutropenia.

Table 3: Pomalidomide Dosage Modifications for cycles ≥ 2

Common Terminology Criteria (CTCAE) Version 4.0	Adverse Event	Dose Change for Pomalidomide
Allergy/Immunology	Allergic reaction/ hypersensitivity (including drug fever) Grade 2	Hold study drug until resolved to \leq Grade 1; Decrease dose by 1 dose level
Allergy/Immunology	Allergic reaction/ hypersensitivity (including drug fever) Grade 3 or 4	Discontinue Study Drug

Common Terminology Criteria (CTCAE) Version 4.0	Adverse Event	Dose Change for Pomalidomide

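### Section 6.5 lets a new cycle start at Grade 2 for non-rash hypersensitivity, while Table 3 holds drug to Grade 1 or less; symptomatic thyroid dysfunction has a similar gap

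*Combined protocol and SAP*

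**What the plan says.** Section 6.5 introduces its checklist with "A new course of treatment may begin on the scheduled Day 1 of a new cycle if" four conditions hold. Two are blood counts (ANC and platelets, each with a baseline alternative). The third is "Any drug-related rash, neuropathy or cardiac event that may have occurred has resolved to" Grade 1 or less, or baseline. The fourth is the catch-all: "Any other drug-related adverse events that may have occurred have resolved to" Grade 2 or less. If the conditions fail, the patient is evaluated weekly, and "A maximum delay of 21 days is allowed for any given cycle".

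Table 3 in Section 6.4.5, headed for cycles 2 and later, has a row for "Allergic reaction/ hypersensitivity (including drug fever) Grade 2". Its action is to hold drug until Grade 1 or less and then go down one dose level. A separate row covers thyroid dysfunction with symptoms: hold, and restart at the prior dose once symptoms have gone and thyroid function is stable.

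Three other parts of Section 6.4.5 matter. It introduces Table 3 as examples. For an interruption that delays a cycle, it says that treatment restarts "when toxicity has resolved as required to allow the start of a new cycle (Section 6.5"), and that the restart day is then Day 1. It also limits holds: "Study drug may be held (up to 21 days) and subsequent dose reductions made as outlined in Table 3", and "If study drug needs to be held > 21 days, the patient is to be taken off study".

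**The concern.** Day 1 of each cycle is when the site decides whether to dose again, and 6.5 is the natural checklist for that decision. Suppose drug fever of Grade 2 begins in Cycle 3 and the drug is held under Table 3. On Cycle 4 Day 1 the fever is still Grade 2 and the counts are adequate. Drug fever is not a rash, a neuropathy or a cardiac event, so it falls under the catch-all, which it passes. A site working from 6.5 would find every condition met and could re-dose during an active reaction, which the Table 3 row is there to prevent. The weekly evaluation in 6.5 would not start either, because it applies only when 6.5's own conditions fail. Section 6.5 also says nothing about the one-level dose reduction.

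The example sits after Cycle 2 on purpose. Table 3 is headed for cycles 2 and later, but the text of 6.4.5 permits interruptions beyond Cycle 2, so Cycle 2 itself is less clear.

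**Working it through.** No sample size, power or error rate is involved. The check sets each Table 3 recovery condition beside the 6.5 start condition that would apply on Day 1.

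**Step 1: sort the Table 3 rows (as they appear in the extracted text).** There are 19 rows. Six discontinue drug: hypersensitivity Grade 3 or 4, arrhythmia Grade 3 or 4, non-desquamating rash Grade 4, desquamating rash Grade 3 or 4, erythema multiforme, and neuropathy Grade 4. Two set no hold: the Grade 2 rash row left to the investigator, and abnormal thyroid tests without symptoms. The remaining 19 − 6 − 2 = 11 hold drug and allow a restart.

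**Step 2: compare the 11 rows with 6.5.**

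| Table 3 row | Table 3 restart condition | 6.5 start condition | Result |
|---|---|---|---|
| Arrhythmia Grade 2 | Grade ≤ 1 | Grade ≤ 1 or baseline | covered |
| Non-desquamating rash Grade 3 | Grade ≤ 1 | Grade ≤ 1 or baseline | covered |
| Neuropathy Grade 2 | Grade ≤ 1 | Grade ≤ 1 or baseline | covered |
| Neuropathy Grade 3 or recurrent Grade 2 | Grade ≤ 1, or baseline if that was Grade 2 | Grade ≤ 1 or baseline | covered |
| **Hypersensitivity Grade 2, non-rash** | **Grade ≤ 1, one level lower** | **Grade ≤ 2 (catch-all)** | **6.5 is looser** |
| Anemia Grade 3 or 4 | Grade ≤ 2 | Grade ≤ 2 (catch-all) | match |
| Other related toxicity Grade 3 or 4 | Grade ≤ 2 | Grade ≤ 2 (catch-all) | match |
| Neutropenia | Grade ≤ 2, or next cycle | ANC condition | tested by count, not grade |
| Thrombocytopenia | Grade ≤ 2, or next cycle | platelet condition | tested by count, not grade |
| Thrombosis/embolism | investigator's discretion | Grade ≤ 2 (catch-all) | 6.5 is not looser |
| **Thyroid dysfunction with symptoms** | **symptoms resolved, function stable** | **Grade ≤ 2 (catch-all)** | **condition not repeated** |

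Five of the 11 rows require Grade 1 or less. The stricter 6.5 condition covers 4 and misses 1. Adding the thyroid row gives 1 + 1 = 2 of 11 where the 6.5 toxicity conditions can be met while Table 3 still holds drug: one on recovery grade, one on a condition not expressed as a grade. The two blood-count rows are not counted, because comparing them further would need the CTCAE count limits, which the documents do not reproduce.

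**Step 3: can the gap be stated in days?** Not as one figure. The 6.4.5 limit counts days held, and in the example the hold began before Day 1. On Schedule A, with a 28-day cycle and drug held from Day d, the days held by the next Day 1 are 28 − d + 1 = 29 − d. The days left under the limit are 21 − (29 − d) = d − 8:

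- hold from Day 8: 0 days left
- hold from Day 15: 7 days left
- hold from Day 22: 14 days left

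On Schedule B, 6.4.5 does not say whether the rest days count as held. So 6.5 permits an immediate start, while Table 3 requires a further hold whose permitted length depends on when the hold began.

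**The case against.** The strongest reply is that the two texts can be obeyed together. Section 6.5 says that a cycle may begin; it does not compel dosing and does not say that a Table 3 hold ends. Table 3 also shows how it ties a hold to the cycle boundary when it means to: the late-cycle neutropenia and thrombocytopenia rows tell the site to begin the next cycle at a lower dose. The hypersensitivity row has no such wording, so its hold most naturally runs on past Day 1. This stands, and it is the better reading. But it is an inference. No text gives Table 3 precedence, Table 3 is introduced as examples, and 6.4.5 cites 6.5 for the recovery needed after a delay.

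A reader might infer from that citation that 6.5 overrides Table 3 at the start of a cycle. The documents do not go so far. The sentence presupposes that an interruption can itself delay a cycle, its main work is to number Day 1, and it does not cancel a hold.

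The circumstances are also narrow. For hypersensitivity, the reaction must be drug-related, non-rash and exactly Grade 2, and must persist to Day 1 despite the hold, with counts adequate. A reaction that shows as rash already needs Grade 1 or less, or baseline, under 6.5, and Grade 3 or 4 hypersensitivity ends treatment. Section 6.2.2 excludes known hypersensitivity to thalidomide or lenalidomide. Section 6.4.5 lets the investigator reduce or stop drug for any adverse event, and Section 6.7 ends treatment for events judged to threaten severe harm. All of this limits the consequence; none of it tells staff which threshold applies.

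**Conclusion.** Wrong as written: an internal inconsistency, of minor severity. Section 6.5 sets a looser Day 1 condition than Table 3 for non-rash hypersensitivity, including drug fever, and omits Table 3's restart condition for symptomatic thyroid dysfunction. Section 6.5 matches all four other Grade 1 recovery rows, so this looks like an omission rather than a choice, and the protocol gives no reason for a looser standard here.

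The effect is confined to dosing safety and consistency in later cycles. Two stronger conclusions might be drawn and are not supported. One is that dose finding is compromised: DLTs are counted in the first cycle (Sections 6.4.1 and 11.1), and the new-cycle rule first applies after it, so the MTD is unaffected. The other is that the rules differ by a fixed 21 days of delay; days already held count against the 6.4.5 limit, so no single figure holds.

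The mismatch in wording is certain. How often it would matter is unknown: the documents give no rate for either event, and enrollment is at most 30. The verdict assumes that some staff would use 6.5 alone as the Day 1 checklist, which the text allows but does not require.

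**What to change.** Make two edits to Section 6.5 in the next amendment.

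1. Extend the list in the Grade 1 condition to *rash, neuropathy, cardiac event or allergic reaction/hypersensitivity (including drug fever)*, and keep its threshold of Grade 1 or less, or baseline.
2. Add: *Any study drug hold under Table 3 continues past Day 1 until its Table 3 restart condition is met.*

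The first edit closes the grade mismatch. The second settles precedence and covers the thyroid row, which the first alone would leave open. The catch-all and the Table 3 rows stay as they are, and the existing 21-day limits in Sections 6.4.5 and 6.5 suffice, so no new off-study rule is needed. The cost is one added term and one sentence, with no new data, visits or patients.

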6.5.1 Treatment compliance

At all times, when dispensing study drug, research center personnel will review the instructions, printed on the packaging, with subjects. Subjects will be asked to maintain a diary to record the drug administration. Subjects will be asked to bring any unused study drug and empty study drug containers to the research center at their next visit. Research personnel will count and record the number of used and unused study drug capsules at each visit and reconcile with the patient diary.

6.6 Concomitant therapy

6.6.1 Recommended concomitant therapy

Subjects should receive full supportive care, including transfusions of blood and blood products, antibiotics, and anti-emetics when appropriate.

6.6.1.1 Anticoagulation Consideration

Pomalidomide increases the risk of thrombotic events in patients who are at high risk or with a history a thrombosis, in particular when combined with other drugs known to cause thrombosis.

Patients are to receive oral aspirin (325mg) as prophylactic anti-thrombotic treatment unless it is contraindicated, or the patient has a platelet count of less than 50,000. If the patient is intolerant of low-dose aspirin and has a platelet count of at least 50,000, the investigator should prescribe therapeutic dose warfarin or low molecular weight heparin. If warfarin is used, close monitoring of the international normalized ratio (INR) is required.

6.6.2 Prohibited concomitant therapy

Concomitant use of sargramostim (GM-CSF), other anti-cancer therapies, including radiation, thalidomide, or other investigational agents is not permitted while subjects are receiving study drug during the treatment phase of the study.

6.7 Discontinuation of Study Treatment

Treatment will continue until occurrence of any of the following events.

- Disease progression
- Adverse event(s) that, in the judgment of the Investigator, may cause severe or permanent harm or which rule out continuation of the treatment regimen.
- Major violation of the study protocol.
- Withdrawal of consent
- Lost to follow up
- Death
- Pregnancy

6.8 Follow-Up

Subjects who discontinue treatment for any reason will be contacted by the site study coordinator at a minimum of every 6 months, until death or 12 months from the last dose of study drug administration, whichever occurs first. At these follow-ups, the study coordinator will collect information about cancer therapies administered after participation in

this study (including dates of treatment), and for survival unless the patient withdraws consent. The information on subsequent treatment and survival status may be obtained without having the subject visit the study center (i.e. phone call). If the information is obtained by phone call then written documentation of the communication must be available for review in the source documents.

At treatment discontinuation, subjects will undergo a safety assessment approximately 30 days (+/- 1 week) post the last dose of study drug. In addition, off study evaluations per the Schedule of Assessments, Section 2 will be done.

7 Adverse events

7.1 Serious Adverse Event (SAE) Definition

An adverse event or suspected adverse reaction is considered “serious” if, in the view of either the investigator or the sponsor, it results in any of the following outcomes:

- Death
- A life-threatening adverse drug experience – any adverse experience that places the patient, in the view of the initial reporter, at immediate risk of death from the adverse experience as it occurred. It does not include an adverse experience that, had it occurred in a more severe form, might have caused death.
- Inpatient hospitalization or prolongation of existing hospitalization
- A persistent or significant incapacity or substantial disruption of the ability to conduct normal life functions.
- A congenital anomaly/birth defect.

Important medical events that may not result in death, be life threatening, or require hospitalization may be considered a serious adverse drug experience when, based upon appropriate medical judgment, they may jeopardize the patient or subject and may require medical or surgical intervention to prevent one of the outcomes listed in this definition. Examples of such medical events include allergic bronchospasm requiring intensive treatment in an emergency room or at home, blood dyscrasias or convulsions that do not result in inpatient hospitalization, or the development of drug dependency or drug abuse (21 CFR 312.32).

- **Important medical events as defined above, may also be considered serious adverse events. Any important medical event can and should be reported as an SAE if deemed appropriate by the Principal Investigator or the IND Sponsor, IND Office.**
- All events occurring during the conduct of a protocol and meeting the definition of a SAE must be reported to the IRB in accordance with the timeframes and procedures outlined in “The University of Texas M. D. Anderson Cancer Center Institutional Review Board Policy for Investigators on Reporting Unanticipated Adverse Events for Drugs and Devices”. Unless stated otherwise in the protocol, all SAEs, expected or unexpected, must be reported to the IND Office, regardless of attribution (within 5 working days of knowledge of the event).

- **All life-threatening or fatal events**, that are unexpected, and related to the study drug, must have a written report submitted within **24 hours** (next working day) of knowledge of the event to the Safety Project Manager in the IND Office.
- **Unless otherwise noted, the electronic SAE application (eSAE) will be utilized for safety reporting to the IND Office and MDACC IRB.**
- **Serious adverse events will be captured from the time of the first protocol-specific intervention, until 30 days after the last study treatment/intervention, unless the participant withdraws consent. Serious adverse events must be followed until clinical recovery is complete and laboratory tests have returned to baseline, progression of the event has stabilized, or there has been acceptable resolution of the event.**
- **Additionally, any serious adverse events that occur after the 30 day time period that are related to the study treatment must be reported to the IND Office. This may include the development of a secondary malignancy.**

Reporting to FDA:

- Serious adverse events will be forwarded to FDA by the IND Sponsor (Safety Project Manager IND Office) according to 21 CFR 312.32.

It is the responsibility of the PI and the research team to ensure that serious adverse events are reported according to the Code of Federal Regulations, Good Clinical Practices, the protocol guidelines, the sponsor's guidelines, and Institutional Review Board policy.

7.2 Adverse Drug Reaction Reporting

Toxicity will be scored using CTCAE Version 4.0 for toxicity and adverse event reporting (see Appendix E). A copy of the CTCAE Version 4.0 can be downloaded from the CTEP homepage (<HTTP://CTEP.INFO.NIH.GOV>). All appropriate treatment areas should have access to a copy of the CTCAE Version 4.0. All adverse clinical experiences, whether observed by the investigator or reported by the patient, must be recorded, with details about the duration and intensity of each episode, the action taken with respect to the test drug, and the patient's outcome. The investigator must evaluate each adverse experience for its relationship to the test drug and for its seriousness.

Abnormal laboratory results will be documented on adverse event worksheets. The investigator must appraise all abnormal laboratory results for their clinical significance. If any abnormal laboratory result is considered clinically significant, the investigator must provide details about the action taken with respect to the test drug and about the patient's outcome. Completed worksheets will be signed by the principal investigator and subsequently scanned into the electronic medical record upon completion of a patient's study participation.

7.3 Pregnancies

Pregnancies and suspected pregnancies (including a positive pregnancy test regardless of age or disease state) of a female subject occurring while the subject is on pomalidomide, or within 4 weeks of the subject's last dose of pomalidomide, are considered immediately reportable events. Pomalidomide is to be discontinued immediately. The pregnancy, suspected pregnancy, or positive pregnancy test must be reported to Celgene Drug Safety immediately by facsimile, or other appropriate method, using the Pregnancy Initial Report Form, or approved equivalent form.

The female subject should be referred to an obstetrician-gynecologist, preferably one experienced in reproductive toxicity for further evaluation and counseling.

The Investigator will follow the female subject until completion of the pregnancy, and must notify Celgene Drug Safety immediately about the outcome of the pregnancy (either normal or abnormal outcome) using the Pregnancy Follow-up Report Form, or approved equivalent form.

If the outcome of the pregnancy was abnormal (e.g., spontaneous or therapeutic abortion), the Investigator should report the abnormal outcome as an AE. If the abnormal outcome meets any of the serious criteria, it must be reported as an SAE to Celgene Drug Safety immediately by facsimile, or other appropriate method, within 24 hours of the Investigator's knowledge of the event using the SAE Report Form, or approved equivalent form.

All neonatal deaths that occur within -28 days of birth should be reported, without regard to causality, as SAEs. In addition, any infant death after 28 days that the Investigator suspects is related to the *in utero* exposure to pomalidomide should also be reported to Celgene Drug Safety immediately by facsimile, or other appropriate method, within 24 hours of the Investigator's knowledge of the event using the SAE Report Form, or approved equivalent form .

Male Subjects

If a female partner of a male subject taking investigational product becomes pregnant, the male subject taking IP should notify the Investigator immediately, and the pregnant female partner should be advised to call their healthcare provider immediately.

7.4 Celgene Drug Safety Contact Information:

Celgene Corporation
Global Drug Safety and Risk Management
[name]
[name]
[name]
[contact]
e-mail: [contact]

7.5 Investigator Reporting Responsibilities

The conduct of the study will comply with all FDA safety reporting requirements.

IND Annual Reports

If the FDA has granted an IND number, it is a requirement of 21 CFR 312.33, that an annual report is provided to the FDA within 60-days of the IND anniversary date. 21 CFR 312.33 provides the data elements that are to be submitted in the report. The Annual Report should be filed with the UTMDACC IND Office, who will then forward it to the FDA. An additional copy should be placed in the study's Regulatory Binder, and a copy provided to Celgene Corporation as a supporter of this study as follows:

Celgene Corporation
Attn: Medical Development
[name]
[name]
[contact]

All adverse experience reports must include the patient number, age, sex, weight, severity of reaction (mild, moderate, severe), relationship to study drug (probably related, unknown relationship, definitely not related), date and time of administration of test medications and all concomitant medications, and medical treatment provided. The investigator is responsible for evaluating all adverse events to determine whether criteria for "serious" and as defined above are present. The investigator is responsible for reporting adverse events to Celgene as described below.

